There is evidence in the literature for altered nociception in patients with FM⁹. FM is also characterized by heightened pain sensitivity to sensory stimuli, possibly as a result of the changes in the central processing in the brain, referred to as central sensitization¹. From a mechanistic perspective, the abnormal efferent activity could be reflected in the affected skeletal muscle. Our study objective is to explore this possibility using image texture feature analysis in B-mode US imaging. We believe that this may be possible since we have previously shown that texture features can not only discriminate between healthy controls and patients with neck pain but also between the two clinical phenotypes of Myofascial Pain Syndrome (MPS), namely groups that contain latent and active myofascial trigger points (MTrPs)¹⁰. Towards this, we propose to use the image texture features to construct a regularized logistic regression model in order to predict and discriminate between healthy controls and fibromyalgia affected muscle.

To summarize, our specific research questions are as follows:

- a. Can a regularized logistic regression model, built on texture variables extracted from B-mode ultrasound images of the upper trapezius discriminate between healthy, and FM subjects? Our hypothesis is that the model should effectively differentiate the two cohorts due to our previous work/success with other chronic pain disorders (MPS).
- b. How does regularization impact the overall performance of the trained model? Our hypothesis is that it should improve its generalizability.
- c. Does the holdout, test data validate the predicted performance of the logistic regression model? Our hypothesis is that it will be within 1 standard error of the prediction mean.

Methods & Design

Study Design:

The study conforms to the Consolidated Standards of Reporting Trials recommendations.

Ethical approval is approved by the University Health Network (UHN) Research Ethics Board.

This study is registered under the National Institutes of Health ClinicalTrials.gov. This proposed study is a diagnostic case-control study with one major independent binary outcome measure (FM present or Healthy), to create 2 patient cohort groups.

Participants:

Recruitment

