All images pre- and post-processing will be performed with MATLAB and the image processing toolbox¹¹. Images will be visually and statistically inspected for quality based on image intensity, contrast, and ability to discriminate muscle fibers. This is necessary to maintain a high standard of imaging data quality, and suspect no more than 15% of the data should be removed due to constraints. Next, since we are analyzing ROI's in the muscle we must extract only a certain number of frames from each video series. We will achieve this using an image filtering method that has been previously used by our group called the CW-SSIM¹² filtering method¹³. It will be used to objectively calculate and extract image frames from each video series in order to obtain the maximal number of images, while still maintaining uniqueness (minimal image overlap). After this procedure is finished we will extract a rectangular ROI estimation of the upper trapezius muscle excluding the upper and lower fascial borders. Lastly, the images will be labelled and organized for further processing.

Feature Extraction

Texture variables will then be extracted from the image ROI's using MATLAB and the image processing toolbox. The features to be extracted are as follows:

1. First order histogram parameters associated with image grayscale. These include mean, standard deviation, skewness, and kurtosis.

2. Gray level co-occurrence matrices (GLCM)¹⁴ will be calculated utilizing 4 directions (0,45,90,135 degrees). 76 variables are then created.
3. Lastly run-length parameters¹⁵ will be determined by gray level run-length matrices based upon the four given directions. Averaging the directions together gives seven features.

In total 88 feature variables will be extracted from each ROI, providing a feature descriptor dataset.

Elastic Net Regularized Logistic Regression

We will then construct and train an elastic net regularized logistic regression model on the dataset using the binary class labels constructed earlier¹⁶. This will be done using MATLAB and the Statistics and Machine Learning Toolbox¹⁷ and performed on a train/test split (80/20) of the original training data. The model will be regularized using the elastic net, which will improve the generalizability of the classification model on unseen data (avoid overfitting problems). The elastic net penalization method also provides a form of variable selection helping to minimize the effect of rank deficiency.

Model Validation

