The model will be validated using 10-fold nested cross validation on the training data due to the fact the model needs hyper-parameter tuning alongside the validation process. This requires a nested procedure where the hyper-parameter tuning is done in an inner loop and the validation of the model is in an outer loop. This will allow for an optimized, trained model that should generalize well to unseen data. This generalization will be tested using the final holdout set and will either confirm or deny whether the constructed model is a good classifier for this task.

Results

After the methodology is applied to all training data, performance metrics can be extracted from the results to demonstrate the model efficacy. Performance metrics like sensitivity, specificity, area under the curve (AUC) and accuracy will be extracted in order to characterize the model performance. These metrics will be averaged across the 10-folds (mean + stdev), and these values will be compared to the final metrics extracted from the holdout test set. If the test set values fall within 1 stdev, it will confirm the accuracy of the performance estimation during the training.

Primary Outcome

The primary outcome measures:

1. Binary classifier discriminates effectively (>70 % accuracy) between the healthy and muscle with FM.
2. Impact of regularization on the model performance.
3. Holdout test validation of the predicted performance.

Discussion

The overarching goal of our research utilizing image texture features is to eventually provide diagnostic aid to clinicians through the usage of clinically feasible, objective and reliable quantitative ultrasound techniques. While computer aided diagnosis research in ultrasound has been heavily explored in areas such as cancer and liver diseases¹⁸⁻²⁰, there has been little to no work in chronic pain¹³. This is the basis for this project proposal utilizing logistic regression modeling with elastic net regularization; the objective is to develop a statistical model with good predictive and diagnostic capabilities.

We are using logistic regression as our classification model due to its efficiency, computational resource requirement, interpretability, input feature scaling invariance, and ease of regularization²¹. The fact that logistic regression intrinsically calculates the predictive probability is a major strength of the model, as other classification techniques require further computationally intensive cross-validation to achieve this.

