Our study has limitations and one of them concerns the generalizability of our findings, since we are evaluating images of the upper trapezius for patients and healthy participants. The upper trapezius muscles may not be representative of the whole patient or the differences between patients who have varying symptomatology and areas of pain. Further research is needed to replicate our findings using muscle groups other than the upper trapezius. We plan to conduct these studies and to correlate our findings with the extent of central sensitization. Another potential limitation is the amount of healthy control recruits available. It is difficult to find participants that do not possess stiffness and myofascial trigger points in their upper trapezius muscle, even among seemingly healthy populations. We suspect this may limit our numbers for this group and fully expect to deal with an unbalanced dataset. There are many methods of compensating for this discrepancy during model construction, training and statistical analysis and will employ them as needed.

In conclusion this study should provide an effective, discriminatory classifier trained on B-mode ultrasound images that can differentiate between healthy muscle and muscle with FM in the upper trapezius. This is one more step in our overarching goal of providing increasingly objective diagnostic tools for clinicians when diagnosing chronic pain disorders.

Acknowledgements: N/A

Declarations

Ethics approval and consent to participate:

Informed consent will be obtained from all subjects participating in this study. Ethical approval was approved by the University Health Network (UHN) Research Ethics Board (Approval

Number: 15-9488.8). The approval form is included in the supplementary files of this submission. This study is registered under the National Institutes of Health ClinicalTrials.gov.

Consent for publication:

Not applicable.

Availability of data and material:

The datasets used and/or analyzed during the study will be available from the corresponding author upon reasonable request.

Data Monitoring Committee

A DMC is not applicable for this study since it is not a multi-location study.

Trial Status:

Protocol version and date: Version 1, Sept. 10, 2019

Recruitment: Completed Sept. 6, 2019

Competing interests:

The authors declare that they have no competing interests.

Funding:

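### The 70% bar in primary outcome 1 is set on raw accuracy, so a shortage of healthy controls can let a weak classifier pass

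*Protocol*

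**What the plan says.** The Primary Outcome section of the protocol lists three outcomes. The first is "Binary classifier discriminates effectively (>70 % accuracy) between the healthy and muscle with FM". This is the only performance level that the protocol sets.

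Other measures are planned. The Results section says: "Performance metrics like sensitivity, specificity, area under the curve (AUC) and accuracy will be extracted in order to characterize the model performance". They are averaged over the ten folds and compared with the holdout values, but none has a level to reach.

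The Study Design section states: "This proposed study is a diagnostic case-control study with one major independent binary outcome measure (FM present or Healthy), to create 2 patient cohort groups". The proportion of FM units is therefore a product of recruitment. On the healthy group, Limitations and Conclusions says: "We suspect this may limit our numbers for this group and fully expect to deal with an unbalanced dataset". The remedy offered there is general: "There are many methods of compensating for this discrepancy during model construction, training and statistical analysis and will employ them as needed".

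The model is trained and tested on divisions of that same dataset ("performed on a train/test split (80/20) of the original training data"). Trial Status records "Recruitment: Completed Sept. 6, 2019".

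**The concern.** Research question (a) asks whether the model can tell FM muscle from healthy muscle. Raw accuracy answers a different question, because it weights sensitivity and specificity by the class shares in the evaluated data. When FM units are the majority, success on FM counts for more than success on controls.

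The mix also acts on the model itself. A logistic model fitted to mostly FM data, with no effective compensation, carries that majority in its intercept and tends to call units FM. Sensitivity rises, specificity falls, and raw accuracy gives most weight to the measure that rose. The label of effective discrimination could then be awarded because controls were scarce. For a study that aims at a diagnostic biomarker, a wrong success label on the first primary outcome matters, even though the other measures are reported.

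**Working it through.** **Inputs.** The threshold, accuracy above 70%, is from Primary Outcome. The direction of imbalance, few healthy controls, is from Limitations and Conclusions. The protocol gives no ratio, group sizes, target sensitivity or specificity, or classification cut-off, so it has no figure of its own to reproduce. The FM:healthy ratios, the AUC and the cut-off rule below are assumptions. All results are expected values without sampling error.

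**Formulas.** For FM:healthy ratio r, the FM share of evaluated units is p = r/(1+r).

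- Accuracy = p × sensitivity + (1 − p) × specificity.
- Balanced accuracy = (sensitivity + specificity)/2.

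Accuracy is a weighted mean of sensitivity and specificity. If both are above 70%, or both at or below it, no mix changes the result. The mix matters only when 70% lies between them.

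**Step 1: a rule with no discrimination.** Calling every unit FM gives sensitivity 1 and specificity 0, so accuracy = p: 50% at 1:1, 66.7% at 2:1, 75% at 3:1 and 80% at 4:1. It passes once p exceeds 0.70, that is r above 0.70/0.30 = 2.33. Balanced accuracy is 50% throughout.

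**Step 2: a weak classifier whose cut-off follows the mix.** Assume scores are normal with equal variance in both groups and means d apart. The cut-off that maximises accuracy is c = d/2 − ln(r)/d on a scale where healthy scores are centred at 0. Then specificity = Φ(c) and sensitivity = Φ(d − c). A curve through sensitivity 85% and specificity 45% has d = Φ⁻¹(0.85) + Φ⁻¹(0.45) = 0.911, and AUC = Φ(d/√2) = 0.74.

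| FM:healthy | Sensitivity | Specificity | Accuracy | Balanced accuracy |
|---|---|---|---|---|
| 1:1 | 67.6% | 67.6% | 67.6% (fails) | 67.6% |
| 1.5:1 | 81.6% | 50.4% | 69.1% (fails) | 66.0% |
| 2:1 | 88.8% | 38.0% | 71.9% (passes) | 63.4% |
| 3:1 | 95.2% | 22.6% | 77.0% (passes) | 58.9% |

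The 3:1 row, for example, is 0.75 × 0.952 + 0.25 × 0.226 = 0.770. The result moves from fail to pass while specificity collapses. At 1.5:1 it does not change.

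**Step 3: a better classifier under the same rule.** A curve through sensitivity 65% and specificity 85% has d = 1.422 and AUC 0.84. Its accuracy is 76.1% at 1:1, 78.6% at 2:1, 81.7% at 3:1 and 84.2% at 4:1. It never fails. Its balanced accuracy, however, falls from 76.1% at 1:1 to 67.5% at 4:1, so balanced accuracy alone is not free of the mix unless the cut-off is also controlled.

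**Step 4: when a false fail can occur.** Hold sensitivity at 65% and specificity at 85% (balanced accuracy 75%). Accuracy is 75.0% at 1:1, 71.7% at 2:1, 70.0% at 3:1 (not above the bar) and 69.0% at 4:1. This needs specificity above sensitivity while FM is the majority, as class weighting might produce.

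**Step 5: cut-off set for equal class weight.** In the same binormal model, c = d/2 makes sensitivity equal specificity. The weak classifier scores 67.6% and the better one 76.1%, whatever the ratio.

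**The case against.** The strongest reply is that the protocol foresees the imbalance and undertakes to compensate for it, including in the statistical analysis, and that the choice of method may properly sit in a SAP that is not shown. Step 5 supports this in part: compensation at training or at the cut-off can largely remove the dependence. What remains is that the protocol itself fixes the criterion. The methods are unnamed and to be used only if required, and nothing ties them to the 70% bar. Rebalancing the training data also does not change how raw accuracy weights the classes in an unbalanced holdout.

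A second reply is that sensitivity, specificity and AUC will expose a one-sided classifier, and that they also enter the comparison of holdout and fold values. Both points are true. A reader might infer that poor performance would be hidden; the documents do not support that. But the comparison tests whether the estimate is reproduced, not whether it is good, so the success label still rests on accuracy alone.

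A third reply concerns direction. A reader might infer that the mix is as likely to fail a good classifier as to pass a poor one, or that it reverses their order. That follows only if sensitivity and specificity stay fixed while the mix changes. Here the model is trained on the same mix, and in steps 2 and 3 the better classifier stays ahead at every ratio and never fails. The false fail in step 4 is possible, but it is a special case.

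Finally, the actual ratio is unknown. That limits any statement about size, not the statement that the criterion depends on it.

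**Conclusion.** The point holds as a risk of a false pass. The only performance bar in the protocol depends on class shares that the protocol expects to be uneven. With no effective compensation, a classifier of AUC 0.74 moves from 67.6% at 1:1 to 71.9% at 2:1 and 77.0% at 3:1, and a rule that calls everything FM passes above about 2.33:1. A false fail of a better classifier is secondary.

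The dependence of accuracy on the mix is an identity. The size of the effect rests on the assumed ratios, the binormal model and the accuracy-maximising cut-off. The effect is small at mild imbalance (no change of result at 1.5:1) and absent when sensitivity and specificity lie on the same side of 70%. The documents do not show that the dataset is in fact unbalanced enough to change the result. The relevant share is that of the units on which accuracy is counted. Because features are taken from each image region ("In total 88 feature variables will be extracted from each ROI, providing a feature descriptor dataset"), that may be an image share rather than the participant ratio.

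The criterion should be corrected before analysis.

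**What to change.** By a dated amendment made before analysis:

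1. Apply the 70% threshold in primary outcome 1 to balanced accuracy, the mean of sensitivity and specificity. At 1:1 this is the same as raw accuracy.
2. Set the classification cut-off within the training data so that both classes carry equal weight, by a class-weighted fit or by a cut-off on predicted probability at the FM share of the training data. Without this, balanced accuracy still shifts with the mix, as step 3 shows.
3. Report raw accuracy descriptively, beside the majority-class share of the evaluated units, and show sensitivity and specificity separately.

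The cost is a short change of wording and a small change to the analysis code; no new data are needed. There are two drawbacks. A primary criterion is reworded after recruitment closed, so the amendment must be dated and must precede analysis. And balanced accuracy can still pass a one-sided classifier: 95% sensitivity with 46% specificity gives (95 + 46)/2 = 70.5%. The two components must therefore be read with it.

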US: Ultrasound

FM: Fibromyalgia

MPS: Myofascial pain syndrome

MTrP: Myofascial trigger points

LASSO: Least absolute shrinkage and selection operator

Background

Fibromyalgia (FM) is a chronic widespread pain disorder characterized by widespread tenderness, psychological distress, fatigue, and sleep disturbance¹. It has an estimated prevalence of 1.1-6.4% of the general population². In the United States, greater disease burden has been reported in FM patients which involve poorer health status, function, sleep, lower productivity, pain-related medications, increased comorbidities and higher costs³. The cause of FM continues to be unknown. The current clinical method of diagnosis of FM is by applying the 2016 FM criteria^{4,5}. These are subjective and do not require a physical examination. Therefore, subjectivity is present when diagnosing FM.

Another method to diagnose FM could be to create a diagnostic biomarker that is objective, reliable and based on the underlying pathophysiology. A biomarker is a characteristic that can be measured objectively to indicate the underlying pathophysiological process⁶. The FDA has identified that qualified biomarkers are one of the following: diagnostic, prognostic, predictive, and pharmacodynamic. “A diagnostic biomarker is a disease characteristic that categorizes a person by the presence or absence of a specific physiological or pathophysiological state or disease”. Our study was designed to create a diagnostic biomarker that could be feasible for clinical utilization and assist in reducing subjectivity and heterogeneity when combined with the current clinical criteria⁴.

From an imaging perspective, there is very little literature available. Magnetic resonance imaging of the muscles in FM patients have been studied in the past which did not show any significant abnormality⁷. Ultrasonography (US) has also been used to study the trigger points found on the outer aspect of the greater trochanter in FM patients⁸. Similarly, this study did not show any significant abnormalities in FM patients. However, the study was limited due to a

small sample size and the absence of a healthy control group. Currently, no study exists to compare FM patients and healthy controls using clinical findings and quantitative US.

Rationale for Utilization of Quantitative Ultrasound

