The experimental protocol will be carried out in the MSK/pain specialty outpatient clinic at Toronto Rehabilitation Institute. Following the completion of the preliminary intake forms and participant debriefing, informed consent will be obtained. Each participant will be seated upright with their hands comfortably on their thighs in a chair that has a high supportive back. They will be asked to relax their neck and shoulder muscles. [name] will then apply the inclusion and exclusion criteria to the patient and assess entry into the study. A research associate, blinded to the clinical status of the study participant, will collect the ultrasound images using a Sonosite X-porte ultrasound system (SonoSite Canada Inc. c/o Visualsonics, [name]) at a depth of 3.0 cm or less and with a linear ultrasonic transducer of 6-15 MHz. The image settings such as depth, sector size, and time gain compensation (TGC), will be kept constant for all participants. The transducer will then be placed perpendicular on the upper trapezius muscle on each side, and its angle was adjusted to acquire the highest quality image. Ultrasound Gel will be used to coat the entire surface of the

transducer before it touched the skin surface. The location on the muscle will be standardized across study participants by being at the midpoint of the muscle belly between the C7 spinous process and the acromioclavicular joint. From that position, the transducer will be moved at a speed of approximately 1 cm/sec toward the acromioclavicular joint to obtain a 10-sec video. One video will be acquired from each side of the muscle group per participant.

Image Pre-processing

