Regularization is a specific technique that is often used as a remedy to solve overfitting in classification models for machine learning²². In a general sense, regularization techniques are used to reduce a model's predictive error on unseen data by minimizing model variance with a given training set by smoothing the predictions. This is done by constraining (regularizing) the regression coefficients towards zero which discourage overly complex (flexible) models. What must be noted is that regularization does not improve the performance of the model on the data it was trained on. More intuitively, regularization acts as a penalty against complexity and steers the model away from memorizing (overfitting) the dataset. For this protocol we are utilizing elastic net regularization (a well-known technique) to improve the performance against the unseen data.

Until now, the literature shows that the diagnosis of FM remains challenging, in part due to its non-specific symptoms, which overlap with many other disorders such as myofascial pain syndrome. Even though patients who present symptoms such as chronic widespread pain, emotional distress, cognitive and sleep disturbances may be formally diagnosed with FM, it is possible that their primary disorder is not FM and has an entirely different pathophysiological mechanism. This protocol should demonstrate the effectiveness of texture analysis techniques when differentiating between FM patients and healthy individuals. Post-image acquisition texture analyses may provide some insight into the pathophysiology underlying FM.

Limitations and Conclusions

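### Research question a is about subjects and primary outcome 1 about muscle, but the only rows the protocol builds are ROIs and nothing combines them, so the >70% accuracy need not answer either

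*Protocol*

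**What the plan says.** The protocol names its target in different ways.

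- **Person.** Research question a asks whether the model can "discriminate between healthy, and FM subjects". The Background motivates the work with a definition: "A diagnostic biomarker is a disease characteristic that categorizes a person by the presence or absence". The Discussion describes the aim as "differentiating between FM patients and healthy individuals".
- **Muscle.** Primary outcome 1 reads "Binary classifier discriminates effectively (>70 % accuracy) between the healthy and muscle with FM".

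The data are built at a third level.

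- **Data Acquisition:** "One video will be acquired from each side of the muscle group per participant".
- **Image Pre-processing:** a similarity filter is used to "extract image frames from each video series in order to obtain the maximal number of images, while still maintaining uniqueness (minimal image overlap"). Images are also removed for quality, with an expected loss of at most 15% of the data. No equal frame count per video or per participant is set.
- **Feature Extraction:** "In total 88 feature variables will be extracted from each ROI, providing a feature descriptor dataset".

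The elastic net model is trained on that dataset. Under Results, sensitivity, specificity, AUC and accuracy are averaged over the 10 folds and compared with the holdout. Neither Model Validation nor Results says over which unit a correct classification is counted.

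**The concern.** The reference standard (2016 FM criteria met, or healthy) exists once per person, and a diagnostic tool is used once per person. The dataset holds many rows per person. If the metrics are computed on its rows, the accuracy is the share of image regions labelled correctly, which is neither the share of participants nor the share of muscles labelled correctly.

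This matters because >70% is the only numerical criterion attached to primary outcome 1. It could be met on ROIs while fewer than 70% of participants are classified correctly, or missed while more than 70% are. The stated criterion would then not answer research question a.

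The point is separate from how data are split. Even if each participant were kept within one fold or partition, ROI accuracy would still not be participant accuracy.

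**Working it through.** **Is there a figure to reproduce?** No. The protocol gives no sample size, frame count or derivation of the 70% mark. All numbers below rest on assumed inputs and show what is possible, not what will happen.

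**Three accuracies.** For participant *i*, let *m_i* be the number of retained ROIs and *a_i* the share of them classified correctly.

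1. ROI accuracy = Σ(m_i·a_i) / Σm_i. This is what the described steps yield.
2. Mean participant share = mean of a_i. It equals (1) when all m_i are equal or, more generally, when m_i and a_i are uncorrelated.
3. Participant accuracy = proportion of participants whose single combined call is right. This is what research question a asks for.

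Going from (1) to (2) removes unequal frame weighting. Going from (2) to (3) is aggregation, and equal frame counts do not remove that step.

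**Constructed examples: a reversal is possible.**

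- Ten participants, 6 wholly right with 24 frames each and 4 wholly wrong with 10 each. ROI: 6×24 / (6×24 + 4×10) = 144/184 = 78.3% (pass). Participants: 6/10 = 60% (fail).
- Eight wholly right with 10 frames each and 2 wholly wrong with 24 each. ROI: 80 / (80 + 48) = 80/128 = 62.5% (fail). Participants: 8/10 = 80% (pass).
- Aggregation alone, equal frames: ten participants with 10 frames each, 6 of each right. ROI: 60/100 = 60%, and the mean share is also 60%. A majority vote is right for 10/10.

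The first two tie frame count perfectly to correctness. They were chosen to flip.

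**Simulation, assumed inputs.** Each participant's probability of a correct ROI has logit drawn from N(0.9, 1.2), where 1.2 is the SD. Frames per participant are uniform on 6-40, drawn independently of accuracy. The participant call is a majority vote with ties counted as wrong. There were 20,000 runs for each number of holdout participants. Entries are the proportion of runs in which the two accuracies fall on opposite sides of 70%.

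| Comparison | N = 10 | N = 20 | N = 30 |
|---|---|---|---|
| ROI vs majority vote, 6-40 frames | 25% | 33% | 41% |
| ROI vs majority vote, 23 frames for all | 26% | 39% | 49% |
| ROI vs mean participant share, 6-40 frames (weighting only) | 12% | 12% | 11% |

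With 6-40 frames, ROI accuracy averaged 66.9% and majority-vote accuracy 74.3%, a gap of about 7 points. With 23 frames for everyone the gap was about 9 points. ROI accuracy and mean participant share did not differ on average.

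**Reading the table.** Equalising the frame counts does not reduce the disagreement, so most of it comes from the missing aggregation step. Unequal weighting alone gives about 11-12%.

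**The case against.** **ROI scoring is inferred.** Results names no unit, and rules for combining frame predictions are often left to a statistical analysis plan, which is not at hand. This stands in part: a reader might infer that the protocol states it will score ROIs, and it does not. But the ROI dataset is the only one it builds and trains on, and research question a and primary outcome 1 name different units within this one document. That mismatch is not a detail deferred elsewhere.

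**Muscle is a legitimate target.** The Abstract, the rationale, primary outcome 1 and the conclusion all speak of muscle. The limitations concede that the upper trapezius may not represent the whole patient, and diagnostic aid is described as an eventual goal. That is fair, and a per-muscle endpoint could be defended. It would still need frames combined within a side, which is not described, and it would leave research question a to be answered separately.

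**Frame weighting may be small.** A reader might infer that the endpoint is distorted mainly by how many frames each video yields, and that yield differs between FM and healthy muscle. The documents do not support this. Video length, transducer speed, starting location and image settings are standardised, which limits variation in yield. Nothing says yield is related to disease or to accuracy. The simulation draws frame counts independently of accuracy, so it cannot show that mechanism.

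**The simulated rule is not the proposed rule.** The simulation uses majority vote, whereas the fix averages probabilities. This stands: no figure is offered for probability averaging.

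**Conclusion.** The concern holds as a mismatch of units. Research question a is about subjects, primary outcome 1 about muscle, and the steps described yield ROI metrics that need not equal the proportion of either classified correctly. The main cause is the lack of aggregation. Unequal frame counts add to it, by an amount and in a direction that cannot be computed without participant and frame counts.

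Under the assumed inputs the 70% conclusion differs between ROI and majority-vote scoring in about 25-49% of runs across the settings tried, with about 11-12% from unequal weighting alone. These percentages depend on the assumed spread of accuracy between participants, the number of holdout participants and the majority-vote rule. They should not be read as the probability of a wrong conclusion in this study.

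Confidence is high for the mismatch and moderate for the crossing of the threshold. It should be fixed before the endpoint is reported, but it does not invalidate the data collected.

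**What to change.** In Results and Primary Outcome 1, make the participant the scored unit, to match research question a:

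1. Average the predicted FM probability over frames within a side, then over the two sides.
2. Derive one classification per participant from that average.
3. Compute accuracy (with the >70% mark), sensitivity, specificity and AUC from these participant results, in the outer folds and in the holdout.
4. Report per-side (muscle) and ROI metrics as secondary, labelled with their unit.

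Averaging within side first also stops a frame-rich video from dominating a participant's result, and scoring once per participant removes frame-count weighting between participants.

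The cost is a few lines of code and protocol wording. No new data are needed; the protocol records recruitment as complete, and the change concerns analysis only. The downside is fewer scored units, so the reported metrics will look less precise.
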